Study Termination/ Individual Study Site Termination	The sponsor may terminate this study prematurely, either in its entirety or at any study site, for reasonable cause provided that written notice is submitted in advance of the intended termination. Advanced notice is not required if the study is stopped due to safety concerns. If the sponsor terminates the study for safety reasons, the sponsor will immediately notify the investigator and subsequently provide written instructions for study termination. If the study has been suspended or terminated, prompt notification will be given to investigators, IRBs, and regulatory authorities in accordance with regulatory requirements.
Statistical Considerations	Efficacy and safety endpoint analysis will be descriptive in nature. Continuous variables will be summarized using number of subjects with mean, standard deviation (SD), median, minimum and maximum. For categorical variables, the number and percentage of subjects in each category will be tabulated.  PK and PD parameters will be summarized using descriptive statistics: number of subjects, mean, median, SD, minimum, maximum, and coefficient of variation, geometric mean and geometric mean SD.  The ESA hyporesponder parallel study will be analyzed separately from the main study.
PK Analysis	A PK analysis will be conducted using non-compartmental analyses to describe vadadustat PK parameters. PK analysis will be reported separately.
PD Analysis	Samples for the PD endpoints (EPO, reticulocytes, iron, Ferritin, hepcidin, and TIBC) will be collected at multiple intervals during the study. An exposure-response analysis of vadadustat, EPO and other PD measures will be conducted as deemed appropriate. PD analysis may be reported separately.
Sample Size Estimation	Approximately 95 subjects are planned for enrollment in the Main study with 40 and 55 subjects randomized to the low epoetin alfa dose group and the high epoetin alfa dose group respectively. Approximately 30 subjects are planned for enrollment in the ESA hyporesponder parallel study. Sample size reflects the exploratory nature of this study.  Enrollment may be increased by up to approximately 20 additional subjects in the Main study, and by up to approximately 30 additional subjects in the ESA hyporesponder parallel study to ensure adequate data are captured for the primary, PK/PD, and safety endpoints.
Safety Monitoring	This is an open label study allowing the study team full access to safety data which will be reviewed on a regular basis, throughout the course of the study. Safety monitoring will be performed as described in the Medical Monitor Plan.

### 3 LIST OF ABBREVIATIONS

AE	adverse event
ALP	alkaline phosphatase
ALT	alanine aminotransferase
aPTT	activated partial thromboplastin time
AST	aspartate aminotransferase
AUC	area under concentration-time curve
AUC inf	area under concentration-time curve from dosing to infinity
AUC last	area under concentration-time curve from dosing to last measurable concentration
BCRP	breast cancer resistance protein
BP	blood pressure
CBC	complete blood count
CKD	chronic kidney disease
CL/F	apparent total body clearance
C max	maximum concentration
CRF	Case Report Form
CRO	Contract Research Organization
CRP	C-reactive protein
DD-CKD	dialysis dependent chronic kidney disease
DME	Designated Medical Event(s)
ECG	electrocardiogram
EDC	electronic data capture
eDiary	electronic diary
EOT	end-of-treatment
EPO	erythropoietin
EQ-5D-5L	EuroQol 5 Dimensions 5 Levels
ESA	erythropoiesis-stimulating agent
ESRD	end-stage renal disease
FAS	Full Analysis Population
FDA	Food and Drug Administration
FSH	follicle stimulating hormone
GCP	Good Clinical Practice
Hb	hemoglobin
HF	heart failure
HIF	hypoxia-inducible factor
HIF-PH	hypoxia-inducible factor prolyl-hydroxylase
HR	heart rate
HRQOL	health-related quality of life
ICH	International Council for Harmonisation of Technical Requirements for Pharmaceuticals for Human Use
INR	International Normalized Ratio
IRB	Institutional Review Board
IV	intravenous
IWRS	Interactive Web Response System

---

LFT	liver function test
LOCF	last observation carried forward
MedDRA	Medical Dictionary for Regulatory Activities
mRNA	messenger ribonucleic acid
NDD-CKD	non-dialysis dependent chronic kidney disease
PGI-C	patient global impression of change
PGI-S	patient global impression of severity
PHD	prolyl 4-hydroxylase domains
PI	Package Insert
PK	pharmacokinetic(s)
PD	pharmacodynamics(s)
PT	Prothrombin Time
RBC	red blood cell
RR	respiratory rate
SAE	serious adverse event
SD	standard deviation
SF-36v2	36-Item Short-Form General Health Survey
SGOT	serum glutamic oxaloacetic transaminase
SGPT	serum glutamic pyruvic transaminase
SOC	System Organ Class
$t_{1/2}$	terminal half life
TIBC	total iron binding capacity
TIW	three times a week
$T_{max}$	time to reach $C_{max}$
TSAT	transferrin saturation
ULN	upper limit of normal
US	United States
$V_d/F$	apparent volume of distribution
VEGF	vascular endothelial growth factor

## 4 BACKGROUND INFORMATION

Chronic kidney disease (CKD), defined as the presence of kidney damage or a decreased level of kidney function, is a major public health problem worldwide. Globally, CKD is estimated to affect between 8% to 16% of the population ([Jha 2013](#); [KDIGO 2013](#)). At the most advanced stages of CKD, end-stage renal disease (ESRD), patients require chronic dialysis or kidney transplantation to sustain life. Chronic kidney disease is not only a cause of ESRD, but is also a significant risk factor for cardiovascular disease, infection, cancer, and mortality ([Iseki 2007](#)).

The prevalence and severity of renal anemia in CKD increases as renal function deteriorates ([Di Iorio 2007](#); [Stauffer 2014](#)). As CKD progresses, the combined effect of decreased red blood cell (RBC) production from lower erythropoietin (EPO) signaling, increased rate of RBC destruction, and reduced iron availability to the bone marrow results in the increased prevalence and severity of anemia ([Pergola 2016](#)). Anemia generally exists when hemoglobin (Hb) is less than 13.0 g/dL in men or less than 12.0 g/dL in women ([KDIGO 2012](#)). Three principal factors contribute to the development of anemia as CKD progresses:

- Peritubular fibroblasts, a type of cell in the kidney, are designed to sense the amount of oxygen carried by the blood. These cells secrete EPO to adjust the production of RBCs by the bone marrow and maintain circulating oxygen levels at normal physiologic levels. As kidney disease progresses, the number of peritubular fibroblasts is reduced and EPO secretion is significantly decreased, leading to a reduction in RBC production ([Iseki 2007](#); [Nurko 2006](#)).
- On average, the RBCs in CKD patients have a shorter lifespan (approximate lifespan of 70 days) compared with the RBCs in healthy people (approximate lifespan of 90 to 120 days) ([Ly 2004](#); [Nurko 2006](#)). Such a condition leads to increased RBC production in CKD patients to maintain normal physiologic levels.
- The availability of iron to the bone marrow is impaired. Iron is a required component in the formation of Hb, and is essential for the transport of oxygen to the tissues of the body.

The main impact of anemia on organ function is reduced oxygen delivery to tissues leading to a constellation of symptoms including fatigue, shortness of breath, and exercise intolerance ([Stauffer 2014](#)). In these patients, compensatory changes occur in cardiac structure and function including an increase in cardiac output and the development of left ventricular hypertrophy and eventually the development of heart failure ([Metivier 2000](#)). Other consequences from anemia in CKD patients include impaired cognitive function, sleep disorders, and depressed immune function which can impact the quality of life in patients ([Iseki 2007](#); [NICE 2011](#)). Overall, anemia contributes to a poorer prognosis in patients with CKD ([Iseki 2007](#); [Nurko 2006](#)).

The risks associated with erythropoiesis-stimulating agents (ESAs), including an increased risk of death and cardiovascular events ([Besarab 1998](#); [Drüeke 2006](#); [Pfeffer 2009a](#); [Pfeffer 2009b](#); [Singh 2006](#)), highlight the need for additional therapies that might minimize or avoid these risks when compared to currently available recombinant protein-based ESAs. Therefore, the unmet medical need for the treatment of anemia in dialysis dependent CKD (DD-CKD) patients remains high. To fulfill this unmet need, the vadadustat clinical program is focused on developing an orally active therapeutic agent for the treatment of anemia in patients with CKD.

#### **4.1 Hypoxia-Inducible Factor Prolyl-Hydroxylase Inhibitors**

*Please see the vadadustat Investigator's Brochure for additional discussion and information for the following section.*

Vadadustat is a synthetic, orally bioavailable, small molecule being developed as an inhibitor of hypoxia-inducible factor prolyl-hydroxylases (HIF-PHs) for the treatment of anemia associated with CKD. HIF-PH enzymes are also referred to as prolyl 4-hydroxylase domains (PHDs), of which the 2 most commonly expressed isoforms are PHD2 and PHD3. Vadadustat is a slightly more potent inhibitor of PHD3 (50% inhibitory concentration [ $IC_{50}$ ] = 0.08  $\mu$ M) than of PHD2 ( $IC_{50}$  = 0.19  $\mu$ M). The inhibition of PHD3 and PHD2 stabilizes hypoxia-inducible factor (HIF)-2 $\alpha$  and HIF-1 $\alpha$ , which in turn stimulates the production of EPO. In vivo animal efficacy and messenger ribonucleic acid (mRNA) data indicate that vadadustat induces the production of EPO from both renal and extra-renal sites (liver and brain), and this increase in EPO results in an increase in RBC production in the bone marrow. In clinical trials, vadadustat has been shown to facilitate iron homeostasis by decreasing hepcidin and increasing transferrin levels in healthy adult male volunteers and male and female CKD patients. This enables iron transport mechanisms that should enhance the terminal steps of erythropoiesis. Vadadustat offers the potential of flexible oral dosing that provides a more gradual and reliable means of titration than injectable hormones. Therefore, vadadustat is being developed as an alternative to the existing protein hormone ESAs.

#### **4.2 Summary of Clinical Experience**

*Please see the vadadustat Investigator Brochure for additional discussion and information for the following section.*

The efficacy, safety, tolerability, pharmacokinetic (PK), and pharmacodynamic (PD) profiles of vadadustat have been characterized in 10 completed Phase 1 studies in healthy volunteers including 1 ethno-bridging study in Caucasian and Japanese subjects, 1 completed Phase 1 study in subjects undergoing chronic hemodialysis, 3 completed Phase 2a studies in non-dialysis dependent CKD (NDD-CKD) subjects, 1 completed Phase 2b study in NDD-CKD subjects, and 1 completed Phase 2 study in DD-CKD subjects. The United States (US) Phase 2a studies evaluated Stages 3, 4, and 5 CKD (not on dialysis) subjects in a single-dose PK study, a multi-dose, 28-day, open-label, dose escalation pilot study, and a randomized, double-blind, placebo-controlled study with 5 different dose groups dosed for 42 days. The US Phase 2b, randomized, double-blind, placebo-controlled study evaluated Stages 3, 4, and 5 CKD (pre-dialysis) dosed for 20 weeks. The Japanese Phase 2, randomized, double-blind, placebo-controlled study evaluated Stages 3, 4, and 5 CKD (pre-dialysis) dosed for 16 weeks. The US Phase 2 open-label study evaluated DD-CKD subjects on chronic hemodialysis dosed for 16 weeks. The Japanese Phase 2, randomized, double-blind, placebo-controlled study evaluated DD-CKD subjects on chronic hemodialysis dosed for 16 weeks. In the studies completed to date, a total of 630 subjects have received vadadustat, including 200 healthy volunteers and 430 subjects with CKD.

Vadadustat has shown dose-dependent increases in EPO concentrations in Phase 1 and Phase 2a studies. The changes in EPO have been accompanied by an increase in reticulocytes and Hb as well as dose responsive increases in total iron binding capacity (TIBC) and decreases in hepcidin and ferritin. Overall, the safety profile for vadadustat has been acceptable and has supported further development. Vadadustat has demonstrated consistent bioavailability with area under

concentration-time curve (AUC) and maximum concentration ( $C_{max}$ ) in Phase 1 and Phase 2 studies covering the dose range of 80 to 1200 mg after single administration and 500 to 900 mg after repeated daily administration for 10 days. The plasma half-life of vadadustat was about 4 to 6 hours, 7 to 8 hours, and 9 to 10 hours in healthy subjects, NDD-CKD patients, and DD-CKD patients, respectively.

Vadadustat is extensively metabolized and its metabolites are eliminated from the body by dual routes of excretion (both renal and fecal). The urinary excretion of vadadustat and its metabolites has been shown to be less than 60% in healthy human volunteers. In a clinical study conducted to evaluate the effect of hemodialysis on the exposures to vadadustat, hemodialysis did not have an effect on the exposures of vadadustat or its metabolites. Given its short half-life and the dual routes of elimination, vadadustat is unlikely to accumulate in patients with CKD.

Multiple doses of 700 and 900 mg daily for up to 10 days (Study AKB-6548-CI-0002 [CI-0002]) and single doses of 1200 mg (Study AKB-6548-CI-0001 [CI-0001], Study AKB-6548-CI-0010 [CI-0010]) have been examined in healthy volunteers. Vadadustat demonstrated dose-proportional PK and achieved serum EPO concentrations up to 34.4 mIU/mL, levels considered physiologic and below exposures achieved with injectable ESAs ([Besarb 1992](#)). A higher incidence of adverse events (AEs) in the gastrointestinal System Organ Class (SOC) – nausea, diarrhea, abdominal pain, dyspepsia – was observed in groups treated with 700, 900, or 1200 mg compared with lower vadadustat doses or placebo. Most AEs were mild to moderate, short-lived (1 or 2 days), and assessed as unrelated by investigators. No AEs led to study withdrawal, and no serious adverse events (SAEs) were reported. No clinically meaningful changes or abnormalities in vital signs, safety laboratory studies, or electrocardiogram (ECG) parameters were reported.

A 16-week, open-label, multicenter, Phase 2 trial evaluated vadadustat in 94 subjects receiving chronic hemodialysis previously maintained on epoetin alfa and IV iron form the 3 months prior to Screening (Study AKB-6548-CI-0011 [CI-0011]). Subjects were assigned to one of three vadadustat dose cohorts: 300 mg daily, 450 mg daily, or 450 mg three times a week (TIW). Dosing was fixed for the first 8 weeks; for the subsequent 8 weeks dose was adjusted from 150 to 600 mg according to Hb response based upon a dose adjustment algorithm. Sixty-nine of the 94 subjects completed the study. The primary endpoint was the mean Hb concentration change from pre-treatment average (Screening Visit 1, Screening Visit 2, and Baseline Visit) to mid-study (Weeks 7 to 8) and end-of-study (Weeks 15 to 16) and was analyzed using observed Hb values (no imputation for missing data). No statistically significant mean change in Hb from pre-treatment average was observed for either of the two time points for any of the three treatment groups.

Among subjects randomized to an initial dose of 300 mg daily, 450 mg daily, or 450 mg TIW, 0% (0 of 30), 3% (1 of 33), and 19% (6 of 31) of subjects withdrew from the study due to worsening anemia, respectively. In a sensitivity analysis using last observation carried forward (LOCF) for the primary efficacy endpoint, no significant mean change in Hb from pre-treatment levels was observed in the 300 mg daily dosing group. At Weeks 15 to 16, modest, statistically significant mean decreases were observed in the 450 mg daily and 450 mg TIW dosing groups.

In a post-hoc univariate analysis of baseline characteristics, higher pre-baseline epoetin alfa dose was associated with a decrease in mean Hb at Weeks 7 to 8 and Weeks 15 to 16 in the dosing cohorts. Subjects who discontinued the study due to worsening anemia had a higher mean pre-

baseline epoetin alfa dose compared with subjects who discontinued due to other reasons or subjects who completed the study.

Based on Phase 1 and Phase 2 study results, vadadustat appears to be a suitable candidate for continued development as a treatment for anemia in patients with CKD.

In the ongoing global Phase 3 and Japanese Phase 3 clinical studies, over 7000 subjects are planned to be treated with vadadustat or comparator.

This study will evaluate efficacy, safety and PK/PD with different vadadustat dosing strategies in hemodialysis subjects converting from epoetin alfa to further characterize the optimal vadadustat regimen. This study is the first study to examine vadadustat doses of 750 and 900 mg in DD-CKD subjects.

#### 4.3 Potential Benefits and Risks

*Please see the vadadustat Investigator's Brochure for additional information.*

Trials of injectable ESAs in patients with anemia secondary to NDD-CKD or DD-CKD have demonstrated an increased risk of cardiovascular events associated with higher Hb targets (Besarab 1998; Singh 2006; Pfeffer 2009a). Post-hoc analyses performed by the Food and Drug Administration (FDA) and others have shown an association between these adverse outcomes and supraphysiologic serum EPO levels and/or Hb oscillations and overshoots (McCullough 2013; Unger 2010). In studies to date, oral vadadustat daily increased mean Hb with few excursions above the target range. In addition, serum EPO levels remained well below those reported with ESAs in the literature. As a result, there is the potential for the investigational drug vadadustat to provide an effective and safe therapeutic option for the treatment of renal anemia.

In addition, vadadustat may enhance iron metabolism and transport. Phase 1 and Phase 2 trials have demonstrated a consistent dose-dependent increase in TIBC and decrease in ferritin and hepcidin. Mechanistic studies have demonstrated that HIF stabilization downregulates the iron absorption regulator hepcidin, and upregulates the iron-mobilizing regulators ferroportin and transferrin (and its receptor) (Peysonnaux 2007). Potential clinical benefits include enhanced erythropoiesis and decreased exogenous iron requirements.

In nonclinical safety studies, the main findings originated from an exaggerated pharmacological response that results in increased erythropoiesis, polycythemia, blood hyperviscosity, and the formation of fibrin thrombi in multiple organs. Early mortality noted in the mouse and rat and moribundity in the dog were due to the sequelae associated with polycythemia. These findings were reproducible across species and studies, dose-dependent and showed reversibility. Dose-limiting toxicity in the exploratory toxicology studies was due to hemoglobinuric nephropathy (rat) and emesis associated with body weight loss (dog).

In completed Phase 1 clinical studies of vadadustat in healthy volunteers, there were low numbers of treatment-emergent AEs. The most frequently reported AEs were in the gastrointestinal disorders (i.e., nausea, diarrhea, abdominal pain, flatulence, dyspepsia) and nervous system disorders (i.e., headache, dizziness) SOC. The majority of AEs were mild to moderate in severity.

The most frequently reported AEs in completed Phase 2 studies of NDD- and DD-CKD subjects were in the following SOCs: gastrointestinal disorders (nausea, diarrhea, vomiting),

cardiovascular disorders (hypertension, hypotension, coronary artery disease), renal (renal failure chronic, renal failure acute), infections and infestations (gastroenteritis, urinary tract infection, pneumonia), and metabolism and nutrition disorders (hyperkalemia, fluid overload). Four deaths occurred in the completed Phase 2 clinical studies.

Identified risks include nausea, diarrhea, vomiting, headache, abdominal pain, and uric acid elevations. Hypersensitivity, hyperkalemia and hypertension have been identified as potential risks and hepatotoxicity has been identified as an important potential risk associated with vadadustat therapy.

Review of safety data from completed Phase 1 and 2 clinical studies, as well as review of accumulating data from ongoing studies, continue to support further development of the vadadustat program.

## 5 STUDY OBJECTIVES AND ENDPOINTS

### 5.1 Primary Objective

To assess the efficacy and safety of daily dosing of vadadustat compared to epoetin alfa for 12 weeks in hemodialysis subjects.

### 5.2 Secondary Objectives

- To assess the efficacy and safety of TIW dosing of vadadustat in selected hemodialysis subjects who have been successfully managed with daily dosing of vadadustat through Week 12
- To evaluate the PK/PD of daily and TIW dosing of vadadustat in hemodialysis subjects compared to epoetin alfa
- To assess the efficacy and safety of several dosing strategies of vadadustat compared to epoetin alfa during a 20-week Treatment Period in hemodialysis subjects

### 5.3 Efficacy Endpoints

#### 5.3.1 Primary Endpoints

The primary endpoint will be the mean change in Hb between Baseline (average pretreatment Hb) and the primary evaluation period (average Hb from Weeks 10 to 12).

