### **6.1.2 Study Treatment Period (Baseline/Day 1 to Week 20)**

For all subjects (Main study and ESA hyporesponder parallel study), the Treatment Period will run from Baseline/Day 1 to Week 20. Dose will be adjusted to achieve and maintain Hb levels within the target range of 10.0 to 11.0 g/dL, inclusive, while targeting the middle of the range and minimizing excursions outside of the target range.

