### 7.2 Inclusion Criteria

Subjects must meet the following inclusion criteria:

1.  $\geq 18$  years of age
2. Receiving chronic, outpatient in-center hemodialysis (TIW) for ESRD for at least 12 weeks prior to Screening
3. Maintained on IV epoetin alfa therapy for 8 weeks prior to and including Screening through SV2
4. Eligibility in the Main study and ESA hyporesponder parallel study is based on the following mean weekly epoetin alfa doses:
  - Main study: Mean weekly epoetin alfa dose  $< 300$  U/kg/week for 8 weeks prior to SV2
  - ESA hyporesponder parallel study: Mean weekly epoetin alfa dose  $\geq 300$  U/kg/week for 8 weeks prior to SV2
5. Two Hb values measured by the central laboratory at least 4 days apart between SV1 and SV2 as indicated below:
  - Main study: 2 Hb values between 8.5 and 11.0 g/dL, inclusive
  - ESA hyporesponder parallel study: 2 Hb values between 8.0 and 10.0 g/dL, inclusive
6. Serum ferritin  $\geq 100$  ng/mL and transferrin saturation (TSAT)  $\geq 20\%$  during Screening
7. Folate and vitamin B12 measurements  $\geq$  lower limit of normal during Screening
8. Hemodialysis adequacy as indicated by single-pool Kt/Vurea  $\geq 1.2$  using the most recent historical measurement within 8 weeks prior to or during Screening
9. Understands the procedures and requirements of the study and provides written informed consent and authorization for protected health information disclosure.

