### **8.4.1 Randomization**

#### Main Study:

Subjects will be randomized to either a vadadustat treatment arm or epoetin alfa treatment arm. Randomization will be stratified by mean weekly epoetin alfa dose calculated over a period of 8 weeks prior to SV2:

- Low epoetin alfa dose group ( $\leq 90$  U/kg/week) or
- High epoetin alfa dose group ( $> 90$  to  $< 300$  U/kg/week)

In the low epoetin alfa dose group, subjects will be randomized in a 3:3:2 ratio to receive either an initial vadadustat daily dose of 450 mg (3 tablets) or 300 mg (2 tablets), or epoetin alfa.

In the high epoetin alfa dose group, subjects will be randomized in a 3:3:3:2 ratio to receive either an initial vadadustat daily dose of 600 mg (4 tablets), 450 mg (3 tablets) or 300 mg (2 tablets), or epoetin alfa.

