#### **11.6 Efficacy Analyses**

The primary efficacy endpoint as well as all other secondary endpoints will be summarized using descriptive statistics (means or proportions) by treatment groups and in total, as well as by study visit and/or analysis period as appropriate. Mean values of Hb as well as selected other efficacy parameters will be plotted across study visits/periods by treatment group.

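### Raw mean change in Hb is the only planned summary of the primary endpoint; in groups of about 10 to 15 it is sensitive to chance baseline differences, and a baseline-adjusted estimate should be added

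*Protocol*

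**What the plan says.** The primary objective is comparative (section 5.1): "To assess the efficacy and safety of daily dosing of vadadustat compared to epoetin alfa for 12 weeks in hemodialysis subjects". A secondary objective in section 5.2 extends the comparison with epoetin alfa to several vadadustat dosing strategies.

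The primary endpoint (section 5.3.1) is the "mean change in Hb between Baseline (average pretreatment Hb) and the primary evaluation period (average Hb from Weeks 10 to 12". Section 11.6 states how it is analysed: "The primary efficacy endpoint as well as all other secondary endpoints will be summarized using descriptive statistics (means or proportions) by treatment groups". The synopsis likewise calls the efficacy analysis descriptive. No covariate, model or group difference is named.

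Dosing is treat-to-target. Section 6.1.2 says of all subjects: "Dose will be adjusted to achieve and maintain Hb levels within the target range of 10.0 to 11.0 g/dL, inclusive", with the midpoint as the aim. Section 6.1.2.2 repeats this for the epoetin arm.

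Entry Hb (section 7.2) is wide relative to that target: "Main study: 2 Hb values between 8.5 and 11.0 g/dL, inclusive" and "ESA hyporesponder parallel study: 2 Hb values between 8.0 and 10.0 g/dL, inclusive".

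Section 8.4.1 stratifies the Main study by mean weekly epoetin dose only. "In the low epoetin alfa dose group, subjects will be randomized in a 3:3:2 ratio", and the ratio in the high dose group is 3:3:3:2. The study schematic gives about 15 subjects per vadadustat starting dose and about 10 on epoetin alfa in each Main stratum, and about 15 per arm in the hyporesponder study.

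**The concern.** When every arm is steered to the same Hb, a subject's change depends partly on where that subject started. Suppose two Main study subjects both reach 10.5 g/dL. The one who entered at 8.5 scores +2.0 and the one who entered at 11.0 scores -0.5, although titration hit the same point in both. A group's raw mean change therefore carries its baseline mix.

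Nothing in the design balances baseline Hb, and nothing in the stated analysis adjusts for it. In groups this small, a chance difference in baseline can be read as a difference between drugs or starting doses. Because no test or interval is planned, readers will judge the arms by the displayed means. Baseline Hb is already measured, so the information needed for adjustment is collected and then left out of the summary.

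**Working it through.** **Group sizes.** The allocation ratios reproduce the schematic.
- Low stratum: 40 × (3, 3, 2)/8 = 15, 15, 10.
- High stratum: 55 × (3, 3, 3, 2)/11 = 15, 15, 15, 10.
- Pooled: 75 vadadustat and 20 epoetin, total 95.

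The protocol states no SD, correlation, alpha or power, so there is no sample-size figure to reproduce. All SDs and correlations below are assumptions.

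**Chance gap in mean baseline Hb.** SE = SD_b × √(1/n1 + 1/n2), and the 95% range is ±1.96 × SE. The upper SD_b is that of an even spread over the Main entry range: (11.0 − 8.5)/√12 = 0.72. The lower value taken is 0.5.

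| Groups | √(1/n1 + 1/n2) | SD_b 0.5 | SD_b 0.72 |
|---|---|---|---|
| 15 v 10 | 0.408 | ±0.40 | ±0.58 |
| 15 v 15 | 0.365 | ±0.36 | ±0.52 |
| 75 v 20 | 0.252 | ±0.25 | ±0.36 |

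For 15 v 10, the probability of a gap above 0.3 g/dL is 14% (SD_b 0.5) to 31% (SD_b 0.72).

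**How much of the gap reaches the change contrast.** With on-treatment SD_f and correlation ρ, the slope of change on baseline is ρ × SD_f/SD_b − 1. With SD_b 0.72 and SD_f 0.9:
- ρ 0.3: 0.375 − 1 = −0.63. A baseline gap of 0.58 shifts the change contrast by 0.36 g/dL.
- ρ 0.5: 0.625 − 1 = −0.38, a shift of 0.22 g/dL.
- ρ 0.7: 0.875 − 1 = −0.13, a shift of 0.07 g/dL.

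Only when follow-up Hb is unrelated to baseline (ρ = 0) does the whole gap pass through.

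**Precision.** Variance of raw change = SD_f² + SD_b² − 2ρ × SD_f × SD_b. Baseline-adjusted variance = SD_f² × (1 − ρ²). With the same SDs (0.81 + 0.5184 = 1.3284; 2 × 0.9 × 0.72 = 1.296):

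| ρ | Raw change | Adjusted | Ratio | Reduction |
|---|---|---|---|---|
| 0.3 | 1.3284 − 0.3888 = 0.9396 | 0.81 × 0.91 = 0.7371 | 0.78 | 22% |
| 0.5 | 1.3284 − 0.6480 = 0.6804 | 0.81 × 0.75 = 0.6075 | 0.89 | 11% |
| 0.7 | 1.3284 − 0.9072 = 0.4212 | 0.81 × 0.51 = 0.4131 | 0.98 | 2% |

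The same reductions are the shares of change variance that baseline explains.

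**Sensitivity to on-treatment spread (SD_b 0.72).** If titration narrows SD_f to 0.5, the variance ratio at ρ 0.3 is 0.41, and the 95% half-width for 15 v 10 falls from 0.60 to 0.38 g/dL. At SD_f 0.8 and ρ 0.3 it falls from 0.72 to 0.61. At SD_f 1.0 and ρ 0.7 the ratio is 1.00, so nothing is gained.

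**Why the stratum belongs in the Main study model.** Of the vadadustat subjects, 30/75 = 40% are in the low stratum, against 10/20 = 50% of the epoetin subjects. The 600 mg starting dose exists only in the high stratum. Section 4.2 reports, from the earlier Phase 2 hemodialysis study, that a higher prior epoetin dose went with a fall in mean Hb. A pooled contrast without the stratum would therefore be confounded with a factor linked to the outcome.

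**The case against.** The strongest objection is that this belongs in the statistical analysis plan, which was not available here. The protocol fixes no model, so it fixes none wrongly, and covariates are commonly left to that plan. Part of this stands: an analysis plan may already adjust. But section 11.6 does not leave the method open. It states descriptive means or proportions by group and does not defer to the analysis plan, as section 11.3 does for the analysis populations.

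A reader might infer that change mostly mirrors baseline. The documents do not show that. Even with equal SDs, where the explained share is (1 − ρ)/2, baseline accounts for 35%, 25% and 15% of change variance at ρ 0.3, 0.5 and 0.7. Nor is reaching target assured. Section 8.4.6 moves the dose one level at a time at the investigator's discretion, and section 4.2 reports mean Hb decreases in two of three groups of the earlier study under LOCF.

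A reader might also infer that raw change is always noisier than an adjusted mean whenever the correlation is below 1. That is false when the SDs differ: with 0.72 and 0.9 the gain vanishes at ρ = 0.72/0.9 = 0.8.

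Other sections soften the problem. The in-target proportion at Weeks 10 to 12 is a key secondary endpoint (section 5.3.2), a composite of Hb rise or in-target Hb follows in section 5.3.2.1, and mean Hb is plotted by visit. These help a reader notice imbalance, but they do not correct the primary summary. Pooling starting doses shrinks the chance gap, yet section 5.2 also asks about the separate dosing strategies.

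**Conclusion.** The point holds as a matter of precision and chance imbalance, and the change is worth making; it is not a fatal flaw in an exploratory Phase 2 study. Raw change is not systematically biased in a randomized comparison within stratum, and the documents support no claim of bias.

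For a single starting dose against epoetin in the Main study (15 v 10), a chance baseline gap of up to ±0.40 to ±0.58 g/dL is plausible, and part of it enters the change contrast. It would be tempting to set this against the 0.5 g/dL in section 5.3.2.1, but that is a within-subject response cut-off and not a between-group margin. At SD_b 0.5 the gap range also stays below it.

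The gain from adjustment ranges from substantial, if titration narrows the on-treatment spread, to nil, if that spread is wide and the correlation high. All of this rests on assumed SDs and correlations.

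**What to change.** In section 11.6 keep the descriptive tables and add, as estimates and not tests:

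> Weeks 10-12 average Hb will be analysed by ANCOVA with treatment group and Baseline Hb (average pretreatment) as covariate, separately for the Main and ESA hyporesponder studies. The Main study model will also include the prior epoetin dose stratum, and starting-dose contrasts with epoetin will be made within stratum (600 mg in the high stratum only). Baseline-adjusted means and vadadustat-minus-epoetin differences with 95% CIs will be reported.

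Use the same model for Weeks 18-20. If the statistical analysis plan already contains this, section 11.6 need only be aligned with it.

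The cost is one extra model per study on data already collected. No subjects or visits are added, and the study stays exploratory. The downside is little or no precision gain if the baseline-to-follow-up correlation is high.
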